Exclusion criteria will be carefully defined to maintain the study's integrity while prioritizing inclusivity. If the subject decides to participate in the study, subjects will be given ample time to review the consent form and ask any questions before signing. Subjects will be given a copy of the informed consent for their reference. Participation in the study is entirely voluntary and they can withdraw at any time without penalty.

Inclusion Criteria

- Male and Female subjects aged 18-75 requiring at least one extraction and replacement with a dental implant.
- No contraindications to dental implant placement

Exclusion Criteria

- Smokers
- Autoimmune disease or disorder
- Neurologic disease or disorder
- Major mechanical obstruction to the mouth opening
- Acute capsulitis
- Bone metabolic disease
- Current systemic antibiotic treatment or within 3 months prior to the study
- Drug addiction or alcohol abuse
- Pregnancy, planning to become pregnant and or nursing
- Type 1 diabetes
- Uncontrolled Type 2 diabetes (Anyone with an A1c $\geq 7\%$)

Enrollment

This single site study is expected to enroll a total of 80-100 subjects.

Data Analysis and Interpretation

All collected data, including personal and medical information, is handled with the highest level of security and confidentiality to uphold the privacy and rights of the participant. The informed consent process, a key component of the protocol, clearly communicates to participants how their data will be treated, emphasizing the commitment to confidentiality. Data collection, storage, and transmission procedures incorporate high-security measures, including encryption and password protection, to prevent unauthorized access. Personally identifiable information is carefully managed, with a focus on anonymization or de-identification wherever possible to minimize the risk of participant identification. The investigators are granted access only on a need-to-know basis, and strict access controls are implemented. Regular monitoring, audits, and compliance checks are conducted to ensure that data confidentiality measures are consistently followed throughout the study, promoting trust among participants and maintaining the integrity of the study. Safeguarding data confidentiality is of utmost importance to uphold the privacy and rights of study participants.

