This study will undertake a comprehensive analysis to compare outcomes across 5 distinct treatment groups. The primary focus will be to evaluate differences in ridge dimensions through dental radiology and also to evaluate soft tissue healing and closure at 2 weeks post-operatively. The goal is to draw conclusive findings regarding the healing of extraction sites, soft tissue thickness, and ridge dimensions.

Compensation to Participants

Participants will not receive any type of compensation or payment for their participation in the study.

Adverse Event Reporting

In the case of an adverse event (AE) or severe adverse event (SAE) directly associated with the study, participants will not be financially responsible for any consequences resulting from their participation in the study. Should a serious AE occur, any associated medical expenses or required interventions will be covered by the research team. The investigators are fully committed to providing support and resources to manage and address any unexpected challenges that may arise, reaffirming the investigators commitment to the ethical and responsible conduct of research.

Adverse event reporting aims to ensure participant safety, facilitate the evaluation of the intervention's safety profile, and contribute to the overall understanding of potential risks associated with blood draws and extraction and implant therapy. When an adverse event (AE) or severe adverse event (SAE) occurs, it will be promptly and accurately documented. The AE or SAE will be classified in nature, severity and relation to the procedure. It will be reported to all parties including the regulatory authority and ethics committee. The subject will be closely followed until the AE or SAE has been resolved. Timely and transparent reporting is essential for maintaining the integrity of the study, protecting participant welfare, and informing regulatory decisions to ensure the ongoing safety and efficacy of medical interventions.

Principle Investigator Safety Monitoring

1.) Adverse Event Monitoring:

- a. Evaluation of any adverse events (AEs) or serious adverse events (SAEs), which are unfavorable or unintended medical occurrences, to determine their nature, severity, and relationship to the intervention.

2.) Data Collection and Analysis:

- a. Continuous collection and analysis of safety-related data including participant health status and reported symptoms, to identify any patterns or trends that may indicate safety concerns.

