- b. Data collection will take place at each procedure visit

3.) Regular Assessments:

- a. Assessment will be conducted at each visit to monitor for potential side effects, complications, or changes in health status related to the intervention.
- b. Each assessment visit will include a CBCT to assess bone levels and intra-oral photographs to evaluate healing.

4.) Compliance with Protocols:

- a. All treatment protocols will be followed, including adherence to safety procedures and guidelines outlined in ethical standards and regulatory requirements.

5.) Communication:

- a. Clear communication with the principal investigator, research staff, and participants to promptly report and address any safety concerns or adverse events.

6.) Ethical Oversight:

- a. Ethical principles and guidelines will be followed to prioritize participant safety and ensure that the research is conducted with the highest standards of integrity.

7.) Regulatory Reporting:

- a. Reporting and monitoring of any adverse events and safety-related data directly to the institutional review boards (IRB) and all related parties.

8.) Risk-Benefit Assessment:

- a. Continued assessment of the overall risk-benefit profile of the intervention to determine whether the potential benefits outweigh the risks and whether any modifications to the study protocol are necessary.

9.) Documentation:

- a. Through documentation of all safety-related information, including adverse events, their resolution, and any actions taken to address safety concerns.

Data Collection

Ensuring data confidentiality is paramount in a research protocol to protect the privacy of participants and maintain the integrity of the study. The protocol outlines rigorous measures to safeguard all collected data, including personal, medical, and potentially sensitive information related to periodontal disease. Key considerations for data confidentiality in a research protocol include:

Informed Consent Process:

Clearly articulate to participants how their data will be handled, emphasizing the importance of confidentiality during the informed consent process. Verbalize the extent to which their information will be anonymized or de-identified to protect their identity.

Resources Available

This study will be facilitated by [name] and [name], both are trained in GCP, HSR, and HIPPA. Staff is also trained in data collection, documentation, and storage.

Early Withdrawal of Subjects

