Ideally, each participant should stay engaged in the study until the mandated follow-up period concludes. Nevertheless, participation in any study is entirely voluntary, and participants retain the right to withdraw at any time without facing penalties or loss of benefits. Possible reasons for discontinuation may encompass but are not restricted to, the following:

- Unacceptable adverse experience
- The subject is lost to follow-up
- Subjects withdraw consent for any reason
- Investigators withdraw in the best interest of the subject(s)
- Replacement of Screen Fails and Early Termination
- Study Termination

For those subjects who discontinue participation early, each subject will be followed for 30 days for adverse event monitoring (serious adverse reactions will be monitored for 90 days) after discontinuation. Monitoring of adverse reactions may be done by telephone at the study site director's discretion.

Interventions

The study will involve the standard ridge preservation procedures in patients requiring at least one extraction and replacement with a dental implant. Data collection will be conducted at each visit. The gathered data will undergo analysis using appropriate statistical methods, with the primary objective of soft tissue thickness, quality of healing, dental implants success rate, and alveolar bone levels after surgical extraction and implant placement following a standardized protocol.

Participants requiring at least one extraction and replacement with a dental implant who wish to participate in this study will have a one of the 5 membrane variations performed during their routine extraction and bone graft. Thus, there will be five treatment groups.

Group 1 (Control): Resorbable Collagen membrane

Group 2: e-PRF as a sole barrier membrane,

Group 3: Layering a solid-PRF membrane over the e-PRF membrane,

Group 4: Fabricating e-PRF intra-orally in gel form as a Bio-Filler, and

Group 5: Fabricating the e-PRF membrane intra-orally under a solid-PRF membrane

Methods

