Once patients are placed in their corresponding group, they will undergo ridge preservation surgery using standard bone allograft particulate mixed with PRF and secured with a membrane of their respective group. Radiographic data will be collected at conclusion of the surgery. Soft tissue thickness will be measured at the buccal and lingual aspect of the tooth. At the two-week post-operative evaluation, intra-oral photographs will be taken and sent to 3 blinded clinicians to rate the quality of healing for each case. After 3 months with new radiographic data, patient will be scheduled for implant placement with a second stage implant procedure scheduled 3 months after placement. Patients will be encouraged (but not required) to stay for 1 year after implant uncovering with peri-implant parameters recorded every 6 months.

Therapeutic Material Preparation

Blood will be collected through an aseptic technique. Using a butterfly needle set and vacutainer tubes.

Extraction Protocol

Atraumatic extractions will be completed to preserve socket walls. Complete degranulation will be completed utilizing curettes and a carbide bur on a slow-speed handpiece. After degranulation sockets will be irrigated and packed with sticky bone utilizing c/c allograft and both solid and liquid PRF. The Bio-Heat device will be utilized to heat the patient's plasma and create the various iterations of the e-PRF membrane in the 4 treatment groups, the control group will receive a resorbable collagen membrane. All membranes will be secured with chromic gut in 3-0 mattress fashion.

Implant Placement Protocol

After CBCT evaluation and implant planning, osteotomies for BioHorizons dental implants will be prepared according to manufacturer's instructions. All implants will be placed utilizing a delayed approach placing the implants 0-.5mm subcrestally with primary closure achieved utilizing 3.0 chromic gut. Prior to implant placement, soft tissue measurements will be taken.

Implant Uncovery Protocol

A 15 Blade will be utilized and full thickness flaps reflected to allow access to the implant platform. Any bone growth over top of the implant will be removed with a highspeed diamond round bur. The cover screw will be removed and stock BioHorizons healing abutment placed. 3.0 Chromic sutures will be utilized in single interrupted fashion.

Post-op evaluations and Implant planning

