Patients will be seen 2 weeks after each procedure to ensure proper healing and any adverse reactions will be recorded. Intra-oral photographs will also be taken at each visit to evaluate wound

healing. 3-months after ridge preservation, patient will be seen for a radiographic evaluation (CBCT) for proper implant planning.

Re-evaluation treatment (not required)

Patients will be encouraged to return every 6 months after the surgery for data collection including probing depths.

Periodontal Maintenance Treatment

Patients will be placed on a 6-month maintenance with data collection (periodontal charting and fasting blood draw) occurring at each maintenance for up to 1-year after implant placement. Patients will also have supragingival scaling completed with curettes and ultrasonic device completed by a trained study personnel. The first maintenance will begin 6 months after the implant uncovering surgery visit until the 1-year follow-up conclusion of the study. The total study from extraction to final follow-up may last up to 2-years.

Study Timeline

Visit 1 - Screening/Baseline

- Informed Consent
- Medical History
- HIPPA Form
- Urine HCG test if applicable
- Inclusion/Exclusion Criteria
- Periodontal charting
- Necessary Radiographs (CBCT)
- Soft tissue measurements
- Intra-oral photographs

Visit 2- Treatment

- Treatment (Extraction Procedure)
- Intra-oral photographs
- Soft tissue measurement
- Necessary radiographs (CBCT)

Visit 3- Post-operative visit

- 2-week post-operative evaluation after surgical procedure.
- Intraoral photographs

Visit 4- Implant planning appointment

- Necessary Radiographs (CBCT)

Visit 5- Treatment

- Treatment (Implant placement)
- Soft tissue measurements
- Intraoral photographs
- Peri-apical radiographs

Visit 6- Post-operative visit

- 2-week post-operative evaluation after surgical procedure.
- Intraoral photographs

Visit 7- Treatment

- Treatment (implant uncovering appointment)
- Necessary radiographs (CBCT)
- Intraoral photographs

Visit 8- Post-operative visit

- 2-week post-operative evaluation after surgical procedure.

Visit 9 (encouraged)- periodontal maintenance (6 months after implant uncovering)

- Supragingival scaling
- Complete periodontal charting
- Necessary radiographs (CBCT)

Visit 10 (encouraged)- periodontal maintenance (12 months after implant uncovering)

- Supragingival scaling
- Complete periodontal charting
- Necessary radiographs (CBCT)

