Use of Extended Platelet-Rich Fibrin Membranes in Comparison to Collagen Membranes for Socket Grafting: Part 2: A Randomized Clinical Trial

Unique Protocol ID: 13180-[name]

Date of Document: 2/2/2025

Principal Investigator: [name]

Brief Title: E-PRF vs Collagen Membranes in Ridge Preservation

Secondary IDs: None

Statistical analysis Plan for evolution Part 2 study:

The sample size was determined based on the expected mean difference in horizontal ridge width (HRW) between independent groups. A mean difference of 2.3 mm with an estimated standard deviation (SD) of 1.1 mm was used for the calculation. To detect a statistically significant difference at an α level of 0.05 with 90% power, a minimum of 11 participants per group was required. Considering an anticipated 20% dropout rate, the final target sample size was set at 14 participants per group.

All statistical analyses were conducted using GraphPad Prism version 10.0 (GraphPad Software, San Diego, CA, USA). Data were first evaluated for normality utilizing the Shapiro-Wilk test. One-way analysis of variance (ANOVA) was used to identify overall differences among the research groups. When ANOVA showed statistical significance, appropriate post hoc tests were performed. Tukey's multiple comparison test was used to compare all possible pairs of group means in the study, where no single control group was defined (i.e., membranes' fabrication and application time). In contrast, Dunnett's post hoc test was used in the analysis involving a defined control group (i.e., collagen) to specifically compare test groups with the control group while controlling for type I error across multiple comparisons. Results were expressed as mean \pm standard deviation (SD), and statistical significance was set at $p < 0.05$.

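### The protocol gives two overlapping but different lists of primary outcomes, and the SAP names no primary and gives horizontal ridge width neither a visit nor a form

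*Protocol*

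**What the plan says.** **Protocol, Data Analysis and Interpretation.** "The primary focus will be to evaluate differences in ridge dimensions through dental radiology and also to evaluate soft tissue healing and closure", the latter at 2 weeks. The next sentence adds thickness, but as an aim and not as a primary outcome: "The goal is to draw conclusive findings regarding the healing of extraction sites, soft tissue thickness, and ridge dimensions".

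**Protocol, Interventions.** Data are to be analysed "with the primary objective of soft tissue thickness, quality of healing, dental implants success rate, and alveolar bone levels after surgical extraction" and implant placement.

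**SAP.** The word primary does not appear. The sizing paragraph begins: "The sample size was determined based on the expected mean difference in horizontal ridge width (HRW) between independent groups". It uses a difference of 2.3 mm and an SD of 1.1 mm. It names no visit and does not say whether HRW is a width at one scan or a change between two. The protocol never uses the term HRW. Groups are compared by one-way ANOVA, followed by Tukey or, where collagen is the control, Dunnett. Results are given as mean and SD, and significance is p < 0.05.

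**Scans available.** The Study Timeline lists CBCT at Visits 1, 2, 4 and 7 and at the optional Visits 9 and 10. Under Methods, "Radiographic data will be collected at conclusion of the surgery", which makes Visit 2 a possible reference scan alongside Visit 1. Under Post-op evaluations, "3-months after ridge preservation, patient will be seen for a radiographic evaluation (CBCT) for proper implant planning" (Visit 4). The safety monitoring section goes further: "Each assessment visit will include a CBCT to assess bone levels and intra-oral photographs to evaluate healing".

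**The concern.** A confirmatory trial needs one result, fixed in advance, on which it stands or falls, or a stated rule for combining several. Here a reader cannot tell which outcome that is, whether one success is enough, or which HRW measurement is meant. Once data are in hand, the headline could be drawn from either list, or from whichever HRW scan and form looks best, each tested at p < 0.05. Tukey and Dunnett do not help, because they adjust for the number of group comparisons within one outcome and not for the number of outcomes, visits or forms.

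A second problem follows from the Interventions list. Implant success is a yes/no outcome for each implant, and the only group comparison the SAP states is ANOVA with mean and SD, which does not suit it.

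**Working it through.** **1. The two lists side by side.**

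| Outcome | Data Analysis and Interpretation | Interventions | SAP |
|---|---|---|---|
| Bone or ridge on radiographs | primary | primary (bone levels) | HRW, for sizing only |
| Early healing | primary (2 weeks, with closure) | primary (quality of healing) | not mentioned |
| Soft tissue thickness | aim only | primary | not mentioned |
| Implant success | absent | primary | not mentioned |

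The real differences are implant success and, by label, soft tissue thickness.

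**2. The SAP's own figures.** Inflating 11 per group for 20% dropout gives 11 / 0.80 = 13.75, so 14, as stated; five groups make 70. The 11 itself does not follow from 2.3 mm and 1.1 mm in a plain two-sided t-test, which needs 6 per group. That is a separate matter and does not affect what follows.

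**3. False-positive illustration.** From the SAP: five groups of 14, ANOVA at 0.05, Dunnett against collagen. Assumed, because the documents are silent: success on any one outcome counts, no true differences, normally distributed outcomes, correlation between outcomes 0 to 0.8. For k independent outcomes the chance of at least one significant ANOVA is 1 - 0.95^k: 0.0975 for k = 2 and 0.1426 for k = 3. Correlated outcomes, and the ANOVA-then-Dunnett rule, were simulated.

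| Continuous outcomes tested | Any significant ANOVA | Any e-PRF v collagen claim (ANOVA, then Dunnett) |
|---|---|---|
| 1 | 5% | about 2.7% |
| 2 | 8-10% | 4.5-5.4% |
| 3 | 10-14% | 6-8% |

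The lower ends are at correlation 0.8 and the upper ends at 0. Two outcomes correspond to the Data Analysis list; three correspond to the Interventions list without implant success.

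If every primary must succeed, the risk cannot exceed that of any single one, so it is at most 5%.

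**4. HRW alone.** Assume correlations of 0.5 to 0.9 between scans. Taking the best of Visit 4 width, change from Visit 1 and change from Visit 2 gives a significant ANOVA in about 13-14% of null trials, and a collagen claim in about 7.5-8%. Choosing between Visit 4 and Visit 7 width gives about 7-9% on the ANOVA.

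Form also governs what the SD means. With equal variances, SD of change = SD of width x sqrt(2(1 - r)). If 1.1 mm is the SD of a width, the SD of a change is 1.1 mm at r = 0.5 and 1.1 x sqrt(0.2) = 0.49 mm at r = 0.9.

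**5. Implant success.** With no failures in one arm of 14, two-sided Fisher's exact test gives p = 0.098 against 4/14 and p = 0.041 against 5/14. Only a difference of about 36 percentage points (5/14) reaches p < 0.05 before any adjustment.

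**The case against.** **The lists largely agree.** Ridge dimensions and bone levels are close, and healing quality is rated by blinded clinicians from 2-week photographs (Methods), so it broadly matches 2-week healing. A reader might infer two wholly contradictory sets of primaries; the text does not support that. The conflict is confined to implant success and the status of soft tissue thickness.

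**Sizing on HRW implies that HRW is primary.** This is a fair inference and the best defence, but neither protocol list singles HRW out. Accepting it still leaves the visit and the form open.

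**The SAP's sequence already limits false claims.** This stands in part. A reader might take 8-14% as the risk of falsely declaring an e-PRF arm different from collagen. Those figures count any significant overall ANOVA. A collagen claim must also pass Dunnett, and with two outcomes its risk is near 5%. It is still about double the risk with one outcome. The ANOVA step also protects less if some arms truly differ, and the SAP does not stop an overall ANOVA result from being reported on its own.

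**The protocol promises appropriate statistical methods.** That leaves room for a test suited to implant success, but neither document names one.

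**The past tense of the SAP.** A reader might infer that the primary was chosen after outcomes were known. The documents do not show this. Tense alone is not evidence, though it is a reason to ask for the date.

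**Conclusion.** The point holds. The protocol's two statements of the primary outcomes differ, the SAP does not settle them, and the one outcome used for sizing has no visit or form. This should be corrected before results are interpreted.

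The size depends on a rule that the documents do not give. If any one outcome suffices, the chance of a spurious result roughly doubles with two outcomes and rises two- to threefold with three, relative to one named primary, whichever event is counted. If all must succeed, there is no inflation. The percentages are illustrations under assumed correlations and no true differences; they are neither bounds nor the trial's actual error rate. The textual finding does not depend on them.

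**What to change.** - **One primary.** In the protocol's Data Analysis and Interpretation and Interventions sections and in the SAP, name HRW, the outcome the trial was sized on.
- **One visit.** Fix it at one CBCT already scheduled, named and justified by the sponsor. The 3-month scan at Visit 4 is the natural candidate, but the documents tie the 2.3 mm to no visit, and Project Design describes a 6-month trial. These need to be reconciled.
- **One form.** State whether HRW is an absolute width or a change and, if a change, from which scan (Visit 1 or the end-of-surgery scan at Visit 2). It must match what the 2.3 mm and 1.1 mm refer to.
- **The other outcomes.** Make them secondary or exploratory. If co-primaries are kept, state either that all must succeed or a fixed testing order with HRW first.
- **Implant success.** Report counts with exact confidence intervals and Fisher's exact test in place of ANOVA.
- **Timing.** If any outcome data had been seen when the primary was chosen, disclose the date of that choice.

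The cost is wording, with no added patients, visits or scans. The downside is that a secondary result can no longer be presented as a primary success, and a choice made after seeing data would have to be reported as post hoc.

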Use of Extended Platelet-Rich Fibrin Membranes in Comparison to Collagen Membranes for Socket Grafting: Part 2: A Randomized Clinical Trial

Unique Protocol ID: 13180-[name]

Date of Document: 2/2/2025

Principal Investigator: [name]

Brief Title: E-PRF vs Collagen Membranes in Ridge Preservation

Secondary IDs: None

Study Protocol:

Abstract

Dental implants are often considered the gold standard to replace missing teeth. Having success with dental implants depends on the hard tissue and soft tissue remaining after tooth extractions. The first step to successful dental implant placement begins with proper socket grafting which includes placing a bone graft and membrane among other biomaterials such as platelet-rich fibrin (PRF) to prevent the collapse of the ridge that occurs after a dental extraction.

While platelet-rich fibrin is commonly utilized for ridge preservation, it is often used in conjunction with a collagen membrane due to the fact that it has a short resorption time lasting roughly 2 weeks. However, recently, it was discovered that by heating the plasma layer and denaturing the albumin, the resorption properties of PRF could be extended from 2 weeks to 4-6 months. This extended platelet-rich fibrin (e-PRF) membrane is a promising replacement to collagen membranes in various surgeries. The investigators previously demonstrated that it is a safe and feasible alternative to conventional membranes with 4 different iterations of applying the novel e-PRF membrane. However, there still lacks a comparative study to traditional collagen membranes and between the 4 different iterations.

Objective

The purpose of this study is to evaluate and compare the effectiveness of 4 different iterations of utilizing e-PRF membranes with a collagen resorbable membrane. Each placement will receive either one of the 4 different variations of e-PRF membranes or a collagen resorbable membrane in alveolar ridge augmentation.

Project Design

This research will be a 6-month randomized and controlled trial involving patients requiring at least one extraction and replacement with a dental implant. Participants will be recruited and randomly allocated to receive either one of the four iterations of using e-PRF membranes or a standard resorbable collagen membrane. All patients will be treated surgically with ridge preservation and dental implant placement using standard bone graft material and one of the membranes determined by their assigned group.

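### Patients are allocated before surgery and nothing conceals the arm from the operator, so the surgical steps common to all five arms can be carried out with the arm known

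*Protocol*

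**What the plan says.** Protocol, Project Design, describes the allocation: "Participants will be recruited and randomly allocated to receive either one of the four iterations of using e-PRF membranes or a standard resorbable collagen membrane". Protocol, Methods, then gives the order: "Once patients are placed in their corresponding group, they will undergo ridge preservation surgery". Protocol, Interventions, makes the membrane part of one procedure, with "one of the 5 membrane variations performed during their routine extraction and bone graft".

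Protocol, Extraction Protocol, describes three steps without distinguishing the arms:

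- Extraction: "Atraumatic extractions will be completed to preserve socket walls".
- Degranulation: "Complete degranulation will be completed utilizing curettes and a carbide bur on a slow-speed handpiece".
- Packing: "After degranulation sockets will be irrigated and packed with sticky bone utilizing c/c allograft and both solid and liquid PRF".

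The arms separate only afterwards, when the heating device is used to "create the various iterations of the e-PRF membrane in the 4 treatment groups, the control group will receive a resorbable collagen membrane".

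The only people described as blinded are the three clinicians who rate the two-week photographs (Protocol, Methods). Protocol, Data Analysis and Interpretation, makes radiographic ridge dimensions part of the primary focus, and the SAP bases its sample size on horizontal ridge width.

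**The concern.** The trial is meant to compare membranes, and the membrane is applied near the end of the operation. What comes before it (how much socket wall survives, how thoroughly the socket is cleaned, how much graft is packed) depends on the operator and can affect ridge width. The protocol itself ties extraction technique to keeping the socket walls.

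A surgeon who knows the arm may do these steps slightly differently from arm to arm without meaning to. A ridge-width difference could then reflect handling of the socket and not the membrane. Blinded reading of the scans would not remove it, because the difference would lie in the socket being imaged. Blinding the photograph raters protects a different outcome. The surgeon must see the membrane eventually, but need not know it while doing steps that do not depend on it.

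**Working it through.** **1. Order of events.**

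| Step | Differs by arm? | Can the arm be known by then? |
|---|---|---|
| Placement in a group (Methods) | – | Yes: it precedes surgery |
| Extraction, degranulation (Extraction Protocol) | No | Yes: no concealment described |
| Graft packing (Extraction Protocol) | Described as the same | Yes: no concealment described |
| Membrane (Extraction Protocol; Interventions) | Yes | Necessarily |

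No sentence says when the surgeon learns the arm. That the surgeon can know it early is inferred from three facts: placement comes first, the membranes are visibly different, and neither concealment nor a late reveal is described.

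**2. Scans that bear on this.** Protocol, Study Timeline, lists a CBCT at Visit 1 and at Visit 2, the extraction visit. Methods has radiographic data taken when surgery ends. Images therefore exist before extraction and after packing. The SAP neither names a baseline scan nor commits to change from baseline or to any comparison of these scans by arm.

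**3. The plan's own figures.** From the SAP: difference 2.3 mm, SD 1.1 mm, α 0.05, power 90%, 11 per group, 20% dropout. The inflation reproduces: 11/(1 − 0.20) = 13.75, so 14. A plain two-sided two-group calculation gives 5 (normal) or 6 (exact t) per group, not 11, and the SAP does not name its method. This point does not depend on it; only the SD and the group sizes are used below.

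**4. Illustration of size.** The shift is an assumption: no true membrane effect, and all four e-PRF arms moved by the same amount *b* against collagen.

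- Standard error of one arm against collagen: 1.1 × √(2/14) = 0.416 mm. So *b* = 0.25 mm is 0.25/0.416 = 0.60 standard errors, and *b* = 0.5 mm is 1.20.
- ANOVA noncentrality: n × *b*² × (4/5)/SD². At 0.25 mm, 14 × 0.0625 × 0.8/1.21 = 0.58; at 0.5 mm, 14 × 0.25 × 0.8/1.21 = 2.31.
- Dunnett rule: claim if |mean difference| exceeds c × s × √(2/n), where s is the pooled SD and the simulated c is about 2.50 at n = 14.

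Probability of at least one claim, by simulation (repeat runs agree to within about half a percentage point):

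| Assumed shift | ANOVA then Dunnett, n = 14 | Dunnett alone, n = 14 | ANOVA then Dunnett, n = 11 |
|---|---|---|---|
| 0 | 2.7–2.8% | 5% | 2.8% |
| 0.25 mm | 5.8% | 10% | 5.1% |
| 0.5 mm | 16–17% | 26% | 13% |

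The 0.5 mm shift is 0.5/2.3 = 22% of the planning difference.

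**5. How much the Visit 2 scan could reveal.** If ridge width on that scan also had SD 1.1 mm (an assumption), collagen (14) against the four e-PRF arms pooled (56) would have standard error 1.1 × √(1/14 + 1/56) = 0.33 mm. The 95% interval would be about ±0.66 mm, wider than either shift above. The scan can show a gross difference in packing but cannot exclude a shift of this order.

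**The case against.** The strongest reply is that the sentence in Methods opens a summary paragraph and is not an allocation procedure, so a late reveal may already be practised. That stands in part. A reader might infer that the surgeon is stated to operate with the arm known; the documents do not say so. They put placement first and describe no concealment, and one sentence from the sponsor would settle it.

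Second, Interventions refers to a standardised protocol and the technique is uniform across arms, which makes a systematic shift less likely. True, but the documents set no measure of wall integrity or of the amount packed.

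Third, the Visit 1 and Visit 2 CBCTs make the problem partly visible. This also stands, within limits: the SAP does not plan to use them, they would not capture degranulation quality, and the Visit 2 scan comes after allocation, so using it as a baseline could carry an arm difference into the baseline.

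Fourth, the size is hypothetical. Agreed: at 0.25 mm the planned two-stage procedure stays near 5%, and only the larger assumption gives marked inflation.

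Fifth, Group 4 uses e-PRF as a gel filler, and Groups 4 and 5 are fabricated intra-orally. Whether the reveal can wait until after packing in those arms cannot be settled from the documents. Extraction and degranulation are common to every arm regardless.

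A reader might also infer that participants could be excluded after extraction with the arm known, because the socket proved unsuitable. The documents do not support building on that: the eligibility criteria contain no socket-wall condition, and only a general provision for investigator withdrawal exists.

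**Conclusion.** The concern holds as an avoidable opportunity for performance bias. The plan as written lets the arm be known during extraction, degranulation and packing, and it plans no check that would show whether handling differed by arm. It does not show that bias occurred or will occur.

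The false-claim figures (about 2.7% with no shift, 5.8% at 0.25 mm, about 16% at 0.5 mm, 14 per arm) are an illustration. They rest on SD 1.1 mm, an equal shift in all four e-PRF arms and no true effect; they do not estimate what this trial will suffer. The conclusion also rests on the inference that the operator can learn the arm at placement. The change is worth making because it is cheap and because the existing scans could not fully correct the problem at analysis.

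**What to change.** Change the order in Protocol, Methods. Assign each participant the next number in a sequentially numbered sealed allocation, and open it for the surgeon only after extraction, degranulation and, where the arm's preparation allows, graft packing. If plasma heating must start earlier, the staff member already preparing the PRF opens the allocation, works out of the surgeon's view and withholds the arm until that point. State the reveal point for each arm and record when it happened. No intra-operative eligibility step should be added, since the documents contain no such criterion.

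Add two sentences to the SAP. All randomised participants are analysed in their allocated arm. Ridge dimensions on the Visit 2 CBCT are compared by arm, alongside Visit 1, as a check on packing; because that scan follows allocation and membrane placement, the comparison is descriptive and is not a baseline adjustment.

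Cost: a change of order with no extra visit; some chair time while e-PRF is prepared; and possibly unused plasma from collagen participants. Blood is needed in every arm anyway, because every graft contains PRF. Preparation times, blood volumes and staff roles are not stated, so the sponsor should confirm feasibility, particularly for Groups 4 and 5. The sample size does not change.
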